12.1.4 Response Criteria

12.1.4.1 Evaluation of Target Lesions

- Complete Response (CR): Disappearance of all target lesions. Any pathological lymph nodes (whether target or non-target) must have reduction in short axis to <10 mm.
- Partial Response (PR): At least a 30% decrease in the sum of the diameters of target lesions, taking as reference the baseline sum diameters.
- Progressive Disease (PD): At least a 20% increase in the sum of the diameters of target lesions, taking as reference the smallest sum on study (this includes the baseline sum if that is the smallest on study). In addition to the relative increase of 20%, the sum must also demonstrate an absolute increase of at least 5 mm. (Note: the appearance of one or more new lesions is also considered progressions).
- Stable Disease (SD): Neither sufficient shrinkage to qualify for PR nor sufficient increase to qualify for PD, taking as reference the smallest sum diameters while on study.

12.1.4.2 Evaluation of Non-Target Lesions

- Complete Response (CR): Disappearance of all non-target lesions and normalization of tumor marker level. All lymph nodes must be non-pathological in size (<10 mm short axis).
- Note: If tumor markers are initially above the upper normal limit, they must normalize for a patient to be considered in complete clinical response.
- Non-CR/Non-PD: Persistence of one or more non-target lesion(s) and/or maintenance of tumor marker level above the normal limits.
- Progressive Disease (PD): Appearance of one or more new lesions and/or *unequivocal progression* of existing non-target lesions. *Unequivocal progression* should not normally trump target lesion status. It must be representative of overall disease status change, not a single lesion increase.

Although a clear progression of “non-target” lesions only is exceptional, the opinion of the treating physician should prevail in such circumstances, and the progression

status should be confirmed at a later time by the review panel (or Principal Investigator).

12.1.4.3 Evaluation of Best Overall Response

The best overall response is the best response recorded from the start of the treatment until disease progression/recurrence (taking as reference for progressive disease the smallest measurements recorded since the treatment started). The patient's best response assignment will depend on the achievement of both measurement and confirmation criteria.

For Patients with Measurable Disease (i.e., Target Disease)

Target Lesions	Non-Target Lesions	New Lesions	Overall Response	Best Overall Response when Confirmation is Required*
CR	CR	No	CR	≥ 4 wks. Confirmation**
CR	Non-CR/Non-PD	No	PR	≥ 4 wks. Confirmation**
CR	Not evaluated	No	PR	
PR	Non-CR/Non-PD/not evaluated	No	PR	
SD	Non-CR/Non-PD/not evaluated	No	SD	Documented at least once ≥ 4 wks. from baseline**
PD	Any	Yes or No	PD	no prior SD, PR or CR
Any	PD***	Yes or No	PD	
Any	Any	Yes	PD	

* See RECIST 1.1 manuscript for further details on what is evidence of a new lesion.
 
** Only for non-randomized trials with response as primary endpoint.
 
*** In exceptional circumstances, unequivocal progression in non-target lesions may be accepted as disease progression.
 
Note: Patients with a global deterioration of health status requiring discontinuation of treatment without objective evidence of disease progression at that time should be reported as
				

“symptomatic deterioration.” Every effort should be made to document the objective progression even after discontinuation of treatment.

For Patients with Non-Measurable Disease (i.e., Non-Target Disease)

Non-Target Lesions	New Lesions	Overall Response
CR	No	CR
Non-CR/non-PD	No	Non-CR/non-PD*
Not all evaluated	No	not evaluated
Unequivocal PD	Yes or No	PD
Any	Yes	PD
* ‘Non-CR/non-PD’ is preferred over ‘stable disease’ for non-target disease since SD is increasingly used as an endpoint for assessment of efficacy in some trials so to assign this category when no lesions can be measured is not advised		

12.1.5 Duration of Response

Duration of overall response: The duration of overall response is measured from the time measurement criteria are met for CR or PR (whichever is first recorded) until the first date that recurrent or progressive disease is objectively documented (taking as reference for progressive disease the smallest measurements recorded since the treatment started).

The duration of overall CR is measured from the time measurement criteria are first met for CR until the first date that progressive disease is objectively documented.

Duration of stable disease: Stable disease is measured from the start of the treatment until the criteria for progression are met, taking as reference the smallest measurements recorded since the treatment started, including the baseline measurements.

12.1.6 Progression-Free Survival

PFS is defined as the duration of time from start of treatment to time of progression or death, whichever occurs first.

13 DATA REPORTING / REGULATORY REQUIREMENTS

Adverse event lists, guidelines, and instructions for AE reporting can be found in Section 7 (Adverse Events: List and Reporting Requirements).

13.1 DATA REPORTING

13.1.1 Method

This study will be monitored by the Clinical Data Update System (CDUS) Version 3.0. Cumulative protocol- and patient-specific CDUS data will be submitted electronically to CTEP on a quarterly basis, either by FTP burst of data or via the CDS web application. Reports are due

January 31, April 30, July 31, and October 31. Instructions for submitting data using the CDUS can be found on the CTEP Web site: (<http://ctep.cancer.gov/reporting/cdus.html>).

13.1.2 Responsibility for Data Submission

Participating sites will enter data into C3D. The coordinating center is responsible for quarterly CDUS submissions for all sites.

14 CTEP MULTICENTER GUIDELINES

This protocol will adhere to the policies and requirements of the CTEP Multicenter Guidelines. The specific responsibilities of the Principal Investigator and the Coordinating Center (Study Coordinator) and the procedures for auditing are presented in **Appendix E**.

- The Principal Investigator/Coordinating Center is responsible for distributing all IND Action Letters or Safety Reports received from CTEP to all participating institutions for submission to their individual IRBs for action as required.
- Except in very unusual circumstances, each participating institution will order DCTD-supplied agents directly from CTEP. Agents may be ordered by a participating site only after the initial IRB approval for the site has been forwarded by the Coordinating Center to the CTEP PIO ([contact]) except for Group studies.

15 CCR MULTI-INSTITUTIONAL GUIDELINES

15.1 IRB APPROVALS

The PI will provide the NIH Intramural IRB with a copy of the participating institution's approved yearly continuing review. Registration will be halted at any participating institution in which a current continuing approval is not on file at the NIH Intramural IRB.

15.2 AMENDMENTS AND CONSENTS

The CCR PI will provide the NIH Intramural IRB with copies of all amendments, consents and approvals from each participating institution.

16 COLLABORATIVE AGREEMENTS

The agent(s) supplied by CTEP, DCTD, NCI used in this protocol is/are provided to the NCI under a Collaborative Agreement (CRADA, CTA, CSA) between the Pharmaceutical Company(ies) (hereinafter referred to as "Collaborator(s)") and the NCI Division of Cancer Treatment and Diagnosis. Therefore, the following obligations/guidelines, in addition to the provisions in the "Intellectual Property Option to Collaborator" (http://ctep.cancer.gov/industryCollaborations2/intellectual_property.htm) contained within the terms of award, apply to the use of the Agent(s) in this study:

1. Agent(s) may not be used for any purpose outside the scope of this protocol, nor can Agent(s) be transferred or licensed to any party not participating in the clinical study. Collaborator(s) data for Agent(s) are confidential and proprietary to Collaborator(s) and shall be maintained as such by the investigators. The protocol documents for studies utilizing Agents contain confidential information and should not be shared or distributed without the permission of the NCI. If a copy of this protocol is requested by a patient or patient's family member participating on the study, the individual should sign a confidentiality agreement. A suitable model agreement can be downloaded from: <http://ctep.cancer.gov>.
2. For a clinical protocol where there is an investigational Agent used in combination with (an)other Agent(s), each the subject of different Collaborative Agreements, the access to and use of data by each Collaborator shall be as follows (data pertaining to such combination use shall hereinafter be referred to as "Multi-Party Data"):
 - a. NCI will provide all Collaborators with prior written notice regarding the existence and nature of any agreements governing their collaboration with NCI, the design of the proposed combination protocol, and the existence of any obligations that would tend to restrict NCI's participation in the proposed combination protocol.
 - b. Each Collaborator shall agree to permit use of the Multi-Party Data from the clinical trial by any other Collaborator solely to the extent necessary to allow said other Collaborator to develop, obtain regulatory approval or commercialize its own Agent.
 - c. Any Collaborator having the right to use the Multi-Party Data from these trials must agree in writing prior to the commencement of the trials that it will use the Multi-Party Data solely for development, regulatory approval, and commercialization of its own Agent.
3. Clinical Trial Data and Results and Raw Data developed under a Collaborative Agreement will be made available to Collaborator(s), the NCI, and the FDA, as appropriate and unless additional disclosure is required by law or court order as described in the IP Option to Collaborator (http://ctep.cancer.gov/industryCollaborations2/intellectual_property.htm). Additionally, all Clinical Data and Results and Raw Data will be collected, used and disclosed consistent with all applicable federal statutes and regulations for the protection of human subjects, including, if applicable, the *Standards for Privacy of Individually Identifiable Health Information* set forth in 45 C.F.R. Part 164.
4. When a Collaborator wishes to initiate a data request, the request should first be sent to the NCI, who will then notify the appropriate investigators (Group Chair for Cooperative Group studies, or PI for other studies) of Collaborator's wish to

contact them.

5. Any data provided to Collaborator(s) for Phase 3 studies must be in accordance with the guidelines and policies of the responsible Data Monitoring Committee (DMC), if there is a DMC for this clinical trial.
6. Any manuscripts reporting the results of this clinical trial must be provided to CTEP by the Group office for Cooperative Group studies or by the principal investigator for non-Cooperative Group studies for immediate delivery to Collaborator(s) for advisory review and comment prior to submission for publication. Collaborator(s) will have 30 days from the date of receipt for review. Collaborator shall have the right to request that publication be delayed for up to an additional 30 days in order to ensure that Collaborator's confidential and proprietary data, in addition to Collaborator(s)'s intellectual property rights, are protected. Copies of abstracts must be provided to CTEP for forwarding to Collaborator(s) for courtesy review as soon as possible and preferably at least three (3) days prior to submission, but in any case, prior to presentation at the meeting or publication in the proceedings. Press releases and other media presentations must also be forwarded to CTEP prior to release. Copies of any manuscript, abstract and/or press release/ media presentation should be sent to:

Email: [contact]

The Regulatory Affairs Branch will then distribute them to Collaborator(s). No publication, manuscript or other form of public disclosure shall contain any of Collaborator's confidential/ proprietary information.

17 STATISTICAL CONSIDERATIONS

17.1 STUDY DESIGN/ENDPOINTS

The primary endpoint of the study is objective response rate (CR+PR) according to RECIST 1.1 criteria for sunitinib monotherapy in patients with advanced thymic malignancies. The cohorts will separately be evaluated in this regard as the primary endpoint for each. All sample size estimates are based on the objective response rate.

Group 1

Based on available results of systemic treatments of thymic carcinoma in the literature it is concluded that an objective response rate consistent with 25% and greater than 5% could be considered better, or at least similar, to what has been shown for chemotherapy in this setting. For thymomas, a target of 30% is being proposed. For each cohort, this study will use a Simon 2-stage design, optimal for thymic carcinomas and MinMax for thymomas, and set the probability for accepting a poor drug to 10% ($\alpha=0.10$) and the probability of rejecting a good drug at 10% ($\beta=0.10$).

For thymic carcinomas, the study will try to rule out a 5% objective response rate ($p_0=0.05$) and target a modest response rate of 25% ($p_1=0.25$). The study will initially enroll 9 evaluable patients with thymic carcinoma; if 0 of the 9 patients demonstrate a partial response then no further patients will be accrued. If 1 or more of the first 9 patients have a response, then accrual would continue until a total of 24 evaluable patients have been treated. A temporary pause in the accrual to the trial may be necessary to ensure that enrollment to the second stage is warranted. If there are 1 to 2 patients with a response in the total of 24 evaluable patients, then this would be an uninterestingly low rate, while if there were 3 or more patients of the 24 who have a response, this would be sufficiently interesting to warrant further study of this agent in later trials. Under the null hypothesis (5% response rate), the probability of early termination in this cohort is 63%. For thymomas, the study will try to rule out a 10% objective response rate ($p_0=0.10$) and target a modest response rate of 30% ($p_1=0.30$). The study will initially enroll 16 evaluable patients with thymoma; if 0 to 1 of the 16 patients demonstrate a partial response then no further patients will be accrued. If 2 or more of the first 16 patients have a response, then accrual would continue until a total of 25 evaluable patients have been treated. A temporary pause in the accrual to the trial may be necessary to ensure that enrollment to the second stage is warranted. If there are 2 to 4 patients with a response in the total of 25 evaluable patients, then this would be an uninterestingly low rate, while if there were 5 or more patients of the 25 who have a response, this would be sufficiently interesting to warrant further study of this agent in later trials. Under the null hypothesis (10% response rate), the probability of early termination in this cohort is 51%.

Group 2

To gain further information about the use of this agent in this specific disease, we would like to treat 15 additional subjects with thymic carcinoma. Effective with Amendment E (version date 05/12/14), up to 15 patients will be enrolled as a small, pilot cohort to obtain preliminary data on efficacy as well as on a small number of exploratory parameters. The prior overall response rate using the original dose and schedule was approximately 26%. This portion of the study would aim to demonstrate if the response rate were similar to that rate in a limited number of patients treated using a modified dosing schedule (50 mg per day for 2 weeks with 1 week off) in order to determine if further, more definitive study would be warranted. With 15 patients, the two-tailed 90% confidence interval about 26% extends approximately $\pm 18.6\%$ and the two-tailed 80% confidence interval about 26% extends approximately $\pm 14.5\%$. Thus, the response rate obtained would be able to only approximately estimate the true response rate, but would be sufficient to be used as a basis for determining if a more definitive study is warranted, and to estimate parameters to consider for the subsequent study. Similarly, with 15 patients, only an approximate estimate of the PFS probabilities can be obtained, but these results could be informally compared to those resulting from the original dose and schedule. A cohort of 15 subjects would also provide adequate patients for exploratory analyses of a variety of pharmacodynamic studies and to study the effect of sunitinib therapy on regulatory T cells (Tregs), exhausted CD8 T cells, myeloid-derived suppressor cells (MDSCs), and Th1/Th2 T cell populations, as well as the exploratory studies of circulating tumor cells, endothelial progenitors, and mature apoptotic endothelial cells applicable to both groups.

17.2 SAMPLE SIZE/ACCRUAL RATE

12-C-0118 used a Simon 2-stage design with an accrual ceiling of 52 (Group 1) based on the assumption that the individual cohorts for thymoma and thymic carcinoma would proceed to the second stage with accrual ceilings of 25 and 24 evaluable patients respectively (plus an additional 3 patients to allow for a small number of inevaluable patients.) However, the results from the study demonstrated only 1 PR in the thymoma cohort among the first 16 evaluable patients, and hence accrual was halted at 16 patients as previously specified and did not proceed to the accrual ceiling of 25 patients for this cohort (2 or more responses needed to be observed to proceed to 25 patients.) However, in the thymic carcinoma cohort more than 1 PR was observed in the first 9 evaluable patients. Hence, accrual proceeded to the second stage with an accrual ceiling of 24 patients in this cohort. The total accrual in study 12-C-0118 was therefore $16+25=41$ patients. Therefore, a total of 11 slots remained unfilled in the original study due to the inability of the thymoma cohort to proceed to the second-stage of accrual.

In Amendment E, (version date 05/12/14), we provide a justification to evaluate sunitinib in patients with thymic carcinoma while discontinuing evaluation of this drug in patients with thymoma. Further, we would like to evaluate sunitinib in thymic carcinoma using a modified dosing schedule in an additional 15 patients (Group 2). Hence, we would like to utilize the 9 unfilled thymoma slots from the original study, add 6 new slots (to obtain 15 slots for the new thymic carcinoma cohort, Group 2) and retain 2 slots for inevaluable patients for an accrual ceiling of $52+6=58$ patients.

It is anticipated that approximately 3 patients per month overall may enroll on this trial. Group 1 accrual was completed in less than two years. Thus, Group 2 accrual should be completed with approximately one additional year, thereby completing overall trial accrual in a total of three years. Progression free and overall survival will also be determined for each group separately, using Kaplan-Meier curves, and reported as a secondary endpoint.

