- In the first group (Group 1), sunitinib will be administered orally using a continuous schedule at 50 mg per day for 4 weeks with 2 weeks off to constitute a 6-week cycle (Schedule 4/2) until disease progression or development of intolerable side-effects.
- In the second group (Group 2), sunitinib will be administered orally using a continuous schedule at 50 mg per day for 2 weeks with 1 week off to constitute a 3-week cycle (Schedule 2/1) until disease progression or development of intolerable side-effects.
- Toxicity will be assessed every cycle by CTCAE Version 5.0
- Tumor response assessments by RECIST 1.1 criteria will be performed every cycle for Group 1 and every other cycle for Group 2 (every 6 weeks) for patients receiving treatment for less than one year, and every two cycles for Group 1 and every four cycles for Group 2 (every 12 weeks) for patients who have been receiving treatment one year or longer.
- Exploratory studies include evaluation of serum VEGFR2, PLGF, IL-4, IL-12, HGF, and b-FGF (Group 1 only); and circulating tumor cells, endothelial progenitors, and mature apoptotic endothelial cells (both groups). In Group 2, regulatory T cells (Tregs), exhausted CD8 T cells, myeloid-derived suppressor cells (MDSCs), and Th1/Th2 T cell populations will also be evaluated. Where tumor samples are available, intra-tumoral immune infiltrate will be assessed (both groups). Exploratory studies apply to NCI only.

TABLE OF CONTENTS

SUMMARY OF PROTOCOL CHANGES.....	Error! Bookmark not defined.
Précis 4	
TABLE OF CONTENTS.....	5
1 OBJECTIVES.....	8
1.1 Primary Objectives.....	8
1.2 Secondary Objectives.....	8
1.3 Exploratory Objectives	8
2 BACKGROUND AND RATIONALE.....	8
2.1 Thymoma and Thymic Carcinoma	8
2.2 Sunitinib Malate.....	11
2.3 Rationale	21
2.4 Exploratory Studies Background	25
3 PATIENT SELECTION	27
3.1 Eligibility Criteria	27
3.2 Exclusion Criteria	29
3.3 Inclusion of Women and Minorities	31
4 REGISTRATION PROCEDURES	32
4.1 Coordinating Center.....	32
4.2 Participating Site.....	32
4.3 Treatment Initiation Timeline.....	32
5 TREATMENT PLAN.....	32
5.1 Agent Administration.....	32
5.2 General Concomitant Medication and Supportive Care Guidelines.....	34
5.3 Duration of Therapy.....	37
5.4 Duration of Follow Up.....	37
5.5 Criteria for Removal from Study	37
6 DOSING DELAYS/DOSE MODIFICATIONS	38
6.1 General Guidance.....	38
6.2 Treatment delays and modifications for administrative needs	38

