1.2 SECONDARY OBJECTIVES

- To determine the progression-free survival (PFS) and overall survival (OS) for sunitinib in patients with relapsed or refractory thymoma (Group 1 only) or thymic carcinoma
- To assess safety and tolerability of sunitinib
- To assess the duration of response to sunitinib

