Due to the rare nature of thymic malignancies, there are no definitive trials which guide the management of these patients. Based on retrospective case series, surgery has been established as the mainstay of treatment of non-metastatic thymoma and thymic carcinoma. Given the relatively slow growth of well differentiated thymomas, surgery also has a role in locally advanced tumors that are not radically resectable and in those that have loco-regionally relapsed. Chemotherapy, before and/or after surgery, and radiation therapy (RT) may be useful in selected patients.³

In patients with unresectable or metastatic disease, chemotherapy is the primary treatment modality.² In general, response rates are higher with combination chemotherapy (in the range of 30-90%) compared with single-agent chemotherapy;² however, no randomized trials have been conducted to date. Over 50% of patients with locally advanced or metastatic thymoma or thymic carcinoma may fail initial therapy and therefore require second-line therapy. Active agents include cisplatin, vincristine, doxorubicin, etoposide, cyclophosphamide and ifosfamide. Widely used first line chemotherapy combinations include cisplatin/etoposide (EP), cisplatin/etoposide/ifosfamide (VIP), cisplatin/ doxorubicin/ cyclophosphamide (PAC) and Cisplatin/ doxorubicin/ cyclophosphamide/ vincristine (ADOC). Biological agents investigated thus far also have variable rates of response, ranging from 0 to 40%. [Table 3](#) summarizes response rates to combination chemotherapy and biologic agents in patients with recurrent or metastatic thymic malignancies who failed prior chemotherapy.

As discussed earlier, thymic carcinomas are associated with poorer response rates, more aggressive clinical course and shorter survival. Results of systemic therapy in patients with recurrent thymic carcinoma have been discouraging with most studies showing minimal to no objective responses and median PFS ranging between 1.4 and 6 months ([Table 3B](#)). In contrast, treatment with sunitinib was associated with a response rate of 23%, a disease control rate of 91% and median PFS of 6.7 months in patients with thymic carcinoma. These results were comparable to those seen in a recently reported clinical trial of carboplatin and amrubicin. It should be noted that almost 60% of patients with thymic carcinoma on this study had received no previous chemotherapy.

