Bevacizumab + Erlotinib	Bedano PM et al (2008) [Abstract]	18	15 mg/kg IV q 3 weeks+ 150 mg q day	THY (11) TC (7)	NR	11 patients had SD	
Aflibercept+ docetaxel	Isambert N et al (2008) [Abstract]	1	NR	THY	NR	PR	
Dasatinib	Chuah C et al (2006)	1	140 mg daily	THY B2	None	PR	Patient also had CML and was in lymphoid blast crisis. Tumor c-Kit staining negative
Sunitinib	Ströbel P et al (2010)	4	50 mg daily continuous	TC	chemotherapy	SD	OS 40 months
			50 mg 4/2; later 4/4,4/6 and 4/8 schedule	TC	chemotherapy	PR	PFS 18 months
			37.5 mg daily	TC	No chemotherapy	PR	PFS 14 months
			50 mg daily 4/2 schedule	TC	chemotherapy	PR	OS 4 months
	Thomas A et al (2013) [Abstract]	38	50 mg daily 4/2 schedule	THY (16) TC (22)	Chemotherapy (median prior chemo = 2) Chemotherapy (median prior chemo = 2)	PR=1; SD=12 PR=5; SD=15	PFS 7.6 mo; OS not reached PFS 6.7 mo; OS 12.6 mo
SU14813	W. Fiedler et al (2010)	2	4/1 schedule	THY	NR	PR	PFS 15.3 and 9.0 months
Imatinib	Buti S et al (2011)	1	400 mg daily	TC	ADOC	SD	PFS 9 months c-KIT exon 11 mutation (Y553N)
Sorafenib	Bisagni G et al (2009)	1	200 mg BID	TC	Surgery PEI IA octreotide	PR after 8 weeks; maintained after 15 months	c-kit exon 17 (D820E) mutation
	Li X et al (2008)	1	Sorafenib	TC	CDC CEIO CEP Paclitaxel	SD	PFS 9 months; Tumor c-Kit and VEGF staining positive
	Diel U et al (2011)	1	Sorafenib	TC	ADOC	PR	PFS 6 months c-KIT exon 9 deletion present

Abbreviations used: PAC: cisplatin, doxorubicin, cyclophosphamide; ChlVPP: chlorambucil, vinblastine, procarbazine and prednisolone; THY: Thymoma;

TC: Thymic carcinoma; NR: not reported; SD: stable disease; PR: partial response; EPI: cisplatin, etoposide, ifosfamide IA: ifosfamide, doxorubicin; CDC: cisplatin, doxorubicin, and cyclophosphamide; CEIO: cisplatin, ifosfamide, endostar, oxaliplatin; CEP: cisplatin, etoposide, pirarubicin; CML: chronic myeloid leukemia; ADOC: Cisplatin (CDDP), doxorubicin, vincristine, cyclophosphamide

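### Does reporting PFS and OS by group mean that Group 1 curves will mix thymoma with thymic carcinoma?

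*Combined protocol and SAP*

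**What the plan says.** The last sentence of section 17.2 reads: "Progression free and overall survival will also be determined for each group separately, using Kaplan-Meier curves, and reported as a secondary endpoint". The Précis defines the groups by schedule: "In the first group (Group 1), sunitinib will be administered orally using a continuous schedule at 50 mg per day for 4 weeks", with two weeks off, against two weeks on and one week off in Group 2. Histology is a second division, inside Group 1 only. The secondary objective in section 1.2 covers PFS and OS "in patients with relapsed or refractory thymoma (Group 1 only) or thymic carcinoma".

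Section 17.1 does ask for an analysis by histology, but for response: "The cohorts will separately be evaluated in this regard as the primary endpoint for each". On Group 2 PFS it says that "these results could be informally compared to those resulting from the original dose and schedule". Section 17.4 names the Kaplan-Meier method for duration of response, PFS and OS and gives no split by histology. Section 17.3 lists no stratification factors.

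**The concern.** Read strictly, the unit for PFS and OS is the schedule. Group 1 would then have one PFS curve and one OS curve drawn from two diseases that the protocol treats as different. It gives each histology its own null rate, target rate and two-stage design, and section 2.1 states that "thymic carcinomas are associated with poorer response rates, more aggressive clinical course and shorter survival". Table 5 agrees: carcinoma shows "PFS 6.7 mo; OS 12.6 mo" and thymoma "PFS 7.6 mo; OS not reached". A pooled OS curve would describe neither population. Set beside Group 2, which is carcinoma only, it would flatter the original schedule, because part of any difference would come from the better prognosis of thymoma. A reader could fairly ask for the split to be written down.

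**Working it through.** **1. Composition of Group 1.** Section 17.2 gives 16 + 25 = 41 patients, so thymoma is 16/41 = 39%. With the Table 5 counts it is 16/38 = 42%. A literal Group 1 curve would be a substantial mixture.

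**2. Which reference section 17.1 has in mind.** The Group 2 paragraph takes a prior response rate of about 26% for the original dose and schedule. Its stated precision reproduces with n = 15:

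- 90%: 1.645 × √(0.26 × 0.74/15) = 18.6 points (stated 18.6)
- 80%: 1.282 × √(0.26 × 0.74/15) = 14.5 points (stated 14.5)

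The Table 5 response rates are:

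- thymic carcinoma: 5/22 = 22.7%
- thymoma: 1/16 = 6.3%
- pooled Group 1: (5 + 1)/(22 + 16) = 6/38 = 15.8%

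The 26% lies near the carcinoma rate and far from the pooled one. As a pooled figure it would need about 0.26 × 38 ≈ 10 responders, and there were 6. The paragraph opens by saying that the 15 further patients have thymic carcinoma. The PFS sentence then uses the same term for the reference, so the natural reading is the Group 1 carcinoma cohort.

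**3. Effect on PFS, the only survival endpoint with a written cross-schedule comparison.** Assume exponential curves with the Table 5 medians (6.7 months carcinoma, 7.6 months thymoma) and weights 25/41 and 16/41:

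S(t) = (25/41) × 2^(−t/6.7) + (16/41) × 2^(−t/7.6)

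- Solving S(t) = 0.5 gives a pooled median of 7.03 months, against 6.7 for carcinoma.
- At 6 months the components are 2^(−6/6.7) = 0.538 and 2^(−6/7.6) = 0.579, so S(6) = 0.554. The shift is 1.6 points.
- For scale, the 95% half-width at 0.538 with 15 uncensored patients is 1.96 × √(0.538 × 0.462/15) = 0.252, or 25 points.

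**4. Effect on OS, as an illustration only.** The thymoma median is not reported. Assume 24 to 60 months, with 12.6 for carcinoma and the same weights:

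- Pooled median: 15.9 months (thymoma 24) to 20.9 months (thymoma 60), against 12.6.
- Pooled 12-month OS: 59.1% to 65.5%, against 2^(−12/12.6) = 51.7%. That is 7 to 14 points.
- Widening the assumed thymoma median to 18 to 120 months widens the pooled median to about 14.4 to 26 months across the two sets of counts (25 and 16, or 22 and 16).

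The direction is secure and the size is not. Sections 17.1 and 17.2 contain no OS comparison between the two groups.

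**5. Duration of response.** The section 17.2 sentence does not cover it, and section 17.4 names a method without a unit. That is silence, not a rule to pool. With one thymoma responder, a separate thymoma estimate would say almost nothing.

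**The case for a change.** The best case for a change is that an analysis rule should state its own unit. Tables 3B and 5 report past results and do not pre-specify an analysis. The requirement for the same disease in section 17.4 governs only comparisons with other published studies. The histology split in section 17.1 is limited to response. Two sentences would settle the matter at no cost in patients or data, and for OS the mixture could mislead.

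The textual part stands: no sentence in sections 17.1 to 17.4 sets PFS or OS by histology within Group 1. The rest carries less weight.

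- The contrast between group as schedule and cohort as histology is not strict. Sections 17.1 and 17.2 both call Group 2 a cohort.
- Requiring separate curves for each group keeps the two schedules apart. It does not prevent a further split.
- A curve mixing the histologies could hardly be set beside published patients with the same disease, as section 17.4 envisages, so that clause points to disease-specific curves.
- The Group 1 results by histology were already in the protocol when Group 2 was added. Writing the split down now would record existing practice, and it would not guard against a choice made after seeing the data.

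**Conclusion.** No change to the plan follows. This is a wording gap that the analysts have already filled sensibly: Table 5 gives Group 1 PFS and OS by histology, Table 3B gives PFS by histology, and the Group 2 paragraph points to carcinoma as its reference. Even if Group 1 were pooled, the one written comparison would move by about 0.3 months in median PFS (7.03 − 6.7) and 1.6 points at 6 months. That is small beside a half-width of about 25 points with 15 patients, in a comparison the plan itself calls informal. OS could move by several months, but the amount rests on an assumed thymoma median and no stated comparison uses it. No stopping rule, test or sample size depends on these curves.

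The PFS and OS figures assume exponential survival, the interim medians in Table 5 and the 25 and 16 weights from section 17.2. The reading of the Group 2 reference rests on its context, since the 26% there does not exactly match the 5/22 = 22.7% in Table 5.
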